### 5.0 Procedures Involved

#### 5.1 Study Design (Overview)

For most participants, the full length of participation is about 2.5-3 hours spread across 13 weeks (intervention is 12 weeks, and an additional week is included as pre-intervention baseline). For a small proportion of participants (n=8-10) who agree to participate in an end-of-study qualitative interview to share their experiences of the study, the full length of participation is about 2.5-3.5 hours.

1. Telephone conversation to discuss study, assess interest and eligibility, answer participant questions, and provide instructions on consent process (30 minutes)
2. Receive consent form via mail. Prior to randomization, complete a baseline assessment via telephone/online survey (30-45 minutes)
3. At week 1 post-randomization, connect with study navigator by telephone to receive information and referrals about tobacco cessation and food assistance (30 minutes)
- 3a. Participants in the intervention arm will receive instructions about funds (5-10 minutes)
4. Week 4 post-randomization, check-in call with study navigator (10-15 minutes) 4a. Participants in the intervention arm receive additional funds (0-1 minute required for participant)
5. Week 8 post-randomization, check in call with study navigator (10-15 minutes)
- 5a. Participants in the intervention arm receive additional funds (0-1 minute required for participant)
6. Week 12 post-randomization, follow-up assessment (30-45 minutes)
7. Post-intervention qualitative interviews (30-45 minutes)

## 5.2 Detailed Description of Procedures

**POTENTIAL PARTICIPANT IDENTIFICATION:** We will use the electronic health record (EHR) to prescreen potential participants for this study. Potential participants will comprise of current patients MetroHealth patients from a total of 7 MetroHealth sites within Cuyahoga county. We will use the EHR to prescreen for age (21 years or older), smoking status as documented in the EHR (documented as currently smoking), and food insecurity status (documented as food insecure based on social determinants of health screening conducted during the most recent visit). Using this list, we will send out a recruitment packet in the mail, consisting of a 1-page study flyer with key information and a copy of the informed consent document, in the form of a non-return cover memo. The flyer will instruct potential participants to contact the study team by telephone for further information about the study, and to see if they qualify.

As needed and based on recruitment rate, the research team will also make telephone calls to follow-up with potential participants, after having sent recruitment letters (i.e., there is no “cold” calling without sending letters beforehand). Using the prescreened list of individuals, we will randomly follow up with individuals on the list until we reach the enrollment target for the wave (n=15-20 enrolled in each wave; 3-4 enrollment waves; 60 participants in total will be recruited for this study).

**RECRUITMENT, CONSENT, and BASELINE SURVEY:** Recruitment will be conducted by telephone, and there will be no face-to-face visits as part of this study. The study coordinator will use a script to inform participants about the research study being conducted, to assess interest in participating, and to conduct an eligibility screening for interested participants. Individuals will be informed prior to the eligibility screening that not all people who are interested will qualify for the study based pre-determined eligibility criteria. For those who are interested, meet eligibility criteria, and wish to participate, the coordinator will go over the consent form, give the opportunity to ask any questions, and after all questions have been addressed, will collect verbal consent. Verbal consent will be documented on REDCap, including an attestation section from the research coordinator collecting consent. All potential participants will have been mailed a hard copy of the consent form (non-return cover memo) at the recruitment phase.

Participants can be sent another copy as needed. After the research team receives verbal consent, the baseline assessment will be conducted by the research coordinator via an online or telephone survey (based on participants' preference) that is expected to last up to 45 minutes.

**RANDOMIZATION, ALLOCATION:** After the baseline telephone (or online) survey is completed, participants will be randomized in the Intervention arm or the Control arm with a 50/50 chance to be randomized in either arm. The study analyst who has no contact with participants will use a computer-generated random number table to assign participants. In either arm, in Week 1 of the study, all participants will be connected to receive usual care for tobacco cessation, based on their preferences. In either arm, the study navigator (a community health worker) will review participant responses from the baseline telephone survey and reach out to all participants by telephone. This conversation may involve referrals to the tobacco quitline, referrals to counseling/classes offered at MetroHealth or in the community (such as Freedom from Smoking classes), nicotine replacement therapy and/or pharmacotherapy as prescribed by their primary care provider. The study navigator will provide linkages and information to the services available to the participant, which will be documented in a semi-structured call log, and used as the basis of following up on use of tobacco cessation services in subsequent telephone check-ins in Week 4 and Week 8.

In either arm, participants also receive information from the study navigator about local food assistance resources available to them, such as a list of food pantries and community meal sites and eligibility information about federal food assistance programs. Provision of this information will also be documented by a semi-structured call log, and will be used as the basis of following up on food assistance resources in subsequent check-ins in Week 4 and Week 8. Information about tobacco cessation and food assistance resources are provided by telephone and/or in writing, which is within the scope of work for a community health worker.

In the Intervention arm only, participants will receive economic food assistance to meet their individual food and grocery needs during the cessation attempt/study period. This is provided on a monthly basis (3 times during the 12 weeks of the study) during Week 1, Week 5, and Week 9.

Participants in the Intervention arm will be provided \$83 per month (for a total of \$250 for the 12 weeks) to partially support the cost of food (i.e., provide short-term food insecurity relief) during the cessation attempt. These funds will be in the form of VISA gift cards, a check, a direct deposit transaction, or a Zelle transaction, depending on the participant's choosing. The check, direct deposit, and Zelle options are processed through PNC Bank's E-payment system. We are NOT collecting any bank information from the participants. The participant will confirm their bank account information with PNC to deposit the funds or mail the check, but the researchers will not see that information.

**Follow-ups:** About 4 weeks after randomization, the study navigator will conduct a general check-in call with all participants by telephone to follow-up on referrals provided and additional referrals needed. The length of the call is anticipated to be 15 minutes. The content/topics and length of discussions will be documented through call logs.

About 8 weeks after randomization, the study navigator will conduct a general check-in call with all participants by telephone to follow-up on referrals provided and additional referrals needed. The length of the call is anticipated to be 15 minutes. The content/topics and length of discussions will be documented through call logs.

Twelve weeks after randomization (end-of-study), the study coordinator will contact participants to complete the follow-up telephone or online REDCap survey, which is expected to last 30-45 minutes.

**END-OF-STUDY QUALITATIVE INTERVIEWS:** Participants who were randomized to the intervention group and have completed the protocol will be invited to participate in an end-of-study qualitative interview to provide more context about food access, and to share their experiences with the intervention.

**Recruitment:** Similar to the recruitment procedures for the overall study, we will first mail an invitation letter to prior participants, who can contact the research team if they are interested and willing to discuss their food access and study intervention experiences through a telephone interview. As needed, we will follow up with a telephone call to the target subsample of participants who were sent invitation letters.

**Consent:** Verbal consent will be documented on REDCap, including an attestation section from the research staff member collecting consent. All potential participants will have been mailed a hard copy of the consent form (non-return cover memo) with their invitation letter. **Qualitative interviews:** Semi-structured, one-on-one interviews will be conducted by telephone or Zoom, and is expected to last 30-45 minutes. The semi-structured interview will ask questions related to participants' food shopping habits and practices, and participants' perceptions about the impact of the economic intervention.

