## 1.0 Objectives

Tobacco use continues to be a leading cause of preventable disease and early death. The majority of people who smoke are interested in quitting and attempt to quit each year, but successfully quitting can be challenging for many reasons. In particular, smoking cessation can be especially hard when smokers are dealing with unmet social and health needs and areas of financial stress, which are disproportionately experienced by low-income smokers. In this study, we extend previous research showing that food insecurity is independently associated with higher odds of smoking and can act as a barrier to quitting smoking. Therefore, we design and test a 12-week intervention to assist food-insecure smokers who are ready and willing to make a quit attempt. Beyond providing the quit assistance that smokers normally receive, the research seeks to address food insecurity in the short-term by providing economic food assistance during the quit attempt that will help to meet food needs. We will adapt a patient navigation model in which a designated study navigator can help bridge resources and referrals related to tobacco cessation and food access, and provide economic food assistance based on individualized needs. We will recruit 60 participants for a 12-week study, and all participants will be smokers who are ready to quit and have recently experienced food insecurity. All participants will receive quit assistance and information on local food assistance resources, and a monthly check-in from the navigator. In addition, half of the participants (n=30) will be randomly assigned to the intervention arm, and will receive economic food assistance to partially meet their food needs and reduce food insecurity during the cessation attempt. We will assess feasibility and acceptability of the intervention, and preliminary outcomes related to smoking cessation, such as the number of quit attempts lasting 24 hours or more and the longest length of abstinence from tobacco. By conducting this study, we seek to understand whether this type of intervention is feasible to conduct, and acceptable to those who participate. The study findings will serve as the basis of future research on understanding and addressing tobacco-related and food insecurity-related health disparities. Our main research question is whether addressing food insecurity specifically during a smoking cessation attempt is helpful for increasing quitting success rates.

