## 6.0 Inclusion and Exclusion Criteria

### 6.1 Screening Process

Participant eligibility will be determined using a screening questionnaire, by the research coordinator. Prior to administering the eligibility questions, all potential participants will be notified that there are specific inclusion criteria for the study, and not everyone will qualify for the study. Potential participants will be notified after the end of the screening questionnaire whether they are eligible or ineligible based on their responses. In some cases, it is possible that eligibility may not be readily apparent. In those cases, potential participants will be informed that their responses will be reviewed by the study PI, and they will be followed up in the next few days.

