## 11.0 Data Analysis Plan

As a pilot study, the primary outcomes pertain to the assessment of feasibility and acceptability, and to derive preliminary estimates of tobacco cessation measures and food security status. We will conduct t-tests and chi-square tests to explore group differences. Feasibility will be assessed by examining the number of participants screened, percent eligible to participate, refusal rate, and attrition rate between baseline and 12-week follow-up. We will examine participants' utilization of resources related to tobacco cessation and food assistance, to examine feasibility of the navigation model. We will gain feedback from the navigator regarding the process of providing referrals and individualized food assistance. We will evaluate acceptability through open-ended questions to elicit participant feedback regarding their perceptions of helpfulness of food assistance in meeting food needs, helpfulness of food assistance specifically during cessation attempt, and additional barriers and facilitators to making a quit attempt or staying quit.

Qualitative interviews will be transcribed and analyzed using inductive and deductive coding process.

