### 11.1 Data Handling and Security

The records for this study are all electronic. No information will be stored in paper files. We are using MetroHealth's REDCap to store all of our data. Audio-recordings of qualitative interviews will be kept in the REDCap file repository until they are transcribed verbatim, removing any identifying information in the transcription process. After that, we will destroy the audio files, and store interview transcript data as a text file. Only authorized personnel assigned to the study will have access to the study on REDCap. All personnel are affiliated with MetroHealth.

We will keep records for 6 years after study completion. Records are stored on REDCap only. Identifiable data on REDCap will be deleted permanently. Dataset that has removed ALL identifiers will be kept

indefinitely. The study coordinator, the P.I., the study navigator, data analyst, and co-investigators will have access to REDCap. All team members are assigned to this study.

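### Does an even chance of either arm conflict with the stated 30 participants in the intervention arm?

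*Combined protocol and SAP*

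**What the plan says.** Section 1.0 (Objectives) plans 60 participants and says that "half of the participants (n=30) will be randomly assigned to the intervention arm". The figure carries no qualifier such as about or target.

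Section 5.2 (Randomization, Allocation) holds the only operative description. Once the baseline survey is complete, "participants will be randomized in the Intervention arm or the Control arm with a 50/50 chance to be randomized in either arm". It adds: "The study analyst who has no contact with participants will use a computer-generated random number table to assign participants". Blocking, stratification, a list with a fixed total and a cap per arm are not mentioned anywhere. Enrolment runs in 3 to 4 waves of 15 to 20.

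On use of the arms, Section 3.0 makes feasibility and acceptability the primary endpoints. Section 11.0 limits the between-arm analysis to one sentence: "We will conduct t-tests and chi-square tests to explore group differences". No power calculation depends on the arm size.

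**The concern.** Section 1.0 gives a flat number and Section 5.2 describes a mechanism that, read literally as 60 coin tosses, seldom delivers it. A reader cannot tell whether the sequence is unrestricted, a single shuffled list of 30 and 30, or permuted blocks. These differ in final arm sizes, in balance if enrolment falls short, and in how easily the next assignment could be guessed.

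Predictability appears to matter because roles overlap. The coordinator uses a script "to assess interest in participating, and to conduct an eligibility screening for interested participants", and twelve weeks after randomization "the study coordinator will contact participants to complete the follow-up telephone or online REDCap survey". Where eligibility is unclear, Section 6.1 says that "potential participants will be informed that their responses will be reviewed by the study PI". Section 11.1 adds: "The study coordinator, the P.I., the study navigator, data analyst, and co-investigators will have access to REDCap". With enrolment in waves, earlier assignments exist while later candidates are still being screened.

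At stake would be the stated arm size, some precision in the exploratory comparisons and, if past assignments were visible and the list restricted, the concealment of upcoming ones.

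**Working it through.** **Inputs.** Total 60 and intervention arm 30 (Section 1.0); probability 0.5 per participant (Section 5.2). Independence of the draws is an assumption, since the protocol does not state it.

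**The plan's own figure.** 60 × 0.5 = 30. The stated arm size is the expected value under an even chance, and the exact value under a 30/30 list.

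**Spread under independent draws.** Let X be the intervention count, Binomial(60, 0.5).

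- SD = √(60 × 0.5 × 0.5) = √15 = 3.87.
- P(X = 30) = C(60,30)/2^60 = 0.103.
- P(34/26 or more uneven) = 0.366; P(36/24 or more uneven) = 0.155; P(37/23 or more uneven) = 0.092.
- Mean departure from 30: 3.08 people.

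**Precision cost.** For a difference in means with equal variances, the variance relative to 30/30 is (1/a + 1/b)/(2/30).

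| Split | Variance factor | Standard error factor |
|---|---|---|
| 34/26 | 1.018 | 1.009 |
| 36/24 | 1.042 | 1.021 |
| 37/23 | 1.058 | 1.028 |

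Averaged over Binomial(60, 0.5), the factor is 1.0176. The effective sample size is 60/1.0176 = 59.0, a loss of about one participant.

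**If enrolment stopped short.** No section plans this; 45 and 50 are illustrative totals. The variance factor is measured against an even split of the same total.

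| Total randomized | Mean gap between arms, independent draws | Mean gap, single 30/30 list | Average variance increase, independent draws | Average variance increase, single list |
|---|---|---|---|---|
| 45 | 5.4 | 2.7 | 2.4% | 0.6% |
| 50 | 5.6 | 2.2 | 2.1% | 0.3% |

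A gap of 8 or more has probability 23% at 45 and 32% at 50 under independent draws. That sounds large, but the average cost is still only about 2% in variance.

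**Predictability.** Take someone who knows every earlier assignment and always guesses the arm that is behind.

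- Independent draws: 50% correct.
- Single shuffled 30/30 list: (30 + 2^59/C(60,30) − 0.5)/60 = 34.37/60 = 57%.
- Permuted blocks, six of size 4 and six of size 6 in random order (simulated): 69%. The gap never exceeds 3.

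**The two sections side by side.** Under a shuffled list of 30 and 30, each participant's marginal chance of the intervention arm is 30/60 = 0.5. Section 5.2 is therefore true under independent draws, a single list and permuted blocks alike. Section 1.0 is exact under either restricted list when all 60 are randomized, and a planning figure under independent draws. No reading makes the two sections inconsistent.

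**The case for a change.** The best case for a change is that it is cheap. The analyst must choose a sequence, the three candidates behave differently, and two or three sentences would record the choice and who may see past assignments. Arm size also has practical effects. At $250 per intervention participant (Section 5.2), the food funds total 30 × 250 = $7,500 at 30 but 36 × 250 = $9,000 at 36, and the qualitative interviews draw only on intervention-arm completers.

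Part of this stands. The randomization type is not named, and stating it would help whoever reports the trial. The rest does not lead to a different plan:

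- The choice of list is a trade-off. Independent draws cannot be guessed. Either restricted list recovers about one participant's worth of precision and raises the guess rate to 57% or 69%. The documents give no basis for preferring one.
- The exposure through REDCap is not shown. Section 11.1 lists who has access but does not say that the allocation list or past assignments are visible to the coordinator or the principal investigator. Section 5.2 gives assignment to an analyst without participant contact and places it after consent and baseline. Under independent draws, knowing past assignments would not help anyone guess the next.
- The coordinator's 12-week contact bears on outcome ascertainment, which the type of list does not affect.
- Replacing 30 with about 30 in Section 1.0 would alter no result.

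**Conclusion.** No change follows. The plan omits a detail that the analyst settles when generating the sequence, and Sections 1.0 and 5.2 agree under any of the usual methods. In the least favourable case, independent draws with all 60 randomized, the split is exactly 30/30 about 10% of the time, the comparison remains unbiased, and the average variance increase is 1.8%, or about one participant in 60. At 36/24, reached or exceeded with probability 15.5%, the variance increase is 4.2%. Feasibility and acceptability, and tests meant only to explore differences, do not depend on an exact 30.

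This rests on equal outcome variances in the two arms and on assignment by an analyst without participant contact, as Section 5.2 states. The trial report should name the type of sequence used and give the achieved arm sizes; this is a matter of reporting.

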### 5.3 Risk Minimization Procedures and Data Collection Materials

To minimize risks related to annoyance or discomfort over study-related assessments (i.e., surveys and check-in calls with the study navigator), we will inform all potential participants that assessments may ask personal questions, and the estimated duration of the assessments. Participants have the option to skip any question that they do not wish to answer in the surveys. To minimize risks related to potential breach of confidentiality of research participants, we will use secure research systems, namely REDCap, for store any research-related information. To minimize any unforeseeable economic risks (e.g., potential theft of the VISA gift cards), we will ask all participants to keep their participation in this study private (such as not posting on social media about participation). All data collection materials include an Eligibility Script, a Baseline/Follow-up Survey, a Call Log, and a Qualitative Interview Document. All of these sources are attached in the IRB submission.

## 5.4 Type of Data Collected and How Data is Obtained

We are collecting both existing and prospective data. Existing data are collected using electronic health records to ascertain potential participants' age, smoking status, and food insecurity screening status. Prospective data are obtained through a baseline and 12-week follow-up survey, collected through REDCap (survey-administered telephone survey, or self-completed survey), and through semi-structured telephone call logs kept by the study navigator.

For end-of-study qualitative interviews, the interviews will be audio-recorded and transcribed verbatim.

